2.4.4.2 Effect of Other Drugs on Rolapitant

Strong CYP3A4 Inducers (e.g., rifampin): significantly reduced plasma concentrations of rolapitant can decrease the efficacy of Rolapitant; avoid use of Rolapitant in patients who require chronic administration of such drugs (25).

2.4.5 Rationale for the Study

The NK1 antagonist aprepitant was approved by the FDA and by the EMA for the prevention of acute and delayed CINV associated with HEC, including high-dose cisplatin, and moderately emetogenic chemotherapy (MEC) when used in combination with a 5-HT3 antagonist and corticosteroid. Although aprepitant is effective, dosage adjustment of concomitantly administered drugs is necessary because aprepitant is a mixed inducer/inhibitor of cytochrome P450 (CYP) 3A4 and also affects other CYP enzymes. Furthermore, aprepitant requires several doses during each cycle of chemotherapy. Rolapitant has been free of clinically

relevant drug interactions in studies conducted to date, has rapid and good brain penetration which may contribute to its quick onset of action, and a long half-life that allows for dosing only once during each cycle of chemotherapy. PET occupancy studies as well as clinical efficacy data support the use of only a single dose of rolapitant to protect patients for 5 days from CINV. Al is a highly emetogenic regimen with the potential for improvement in delayed nausea/vomiting with rolapitant in addition to 5HT3RA and steroids.

2.4.6 Study Update

To date, 28 patients have been enrolled on to this study, all of them have completed more than 1 cycle of treatment. The treatment of Rolapitant is well tolerated. In the first cohort- Cohort 1 (dexamethasone 12 mg on day 1, and 8 mg on days 2-5), none of the 9 patients had complete response in days 1-10. Since there is no interaction between Rolapitant and CYP3A4, the amendment 2 was written to keep the dose of dexamethasone constant at 12 mg on Days 2-5 for Part 1 (Rolapitant). In this new cohort- Cohort 2 (dexamethasone 12 mg on days 1-5), the complete response rate (no emetic episodes and no rescue medications) was 29% (5/19) in days 1-10; and the complete response rate was 32% (6/19) for emetic episodes only related to chemotherapy. We therefore would like to expand our experience with the current regimen to confirm the response rate prior to initiation of Part 2 of the study.

3.0 Background Drug Information

3.1 Rolapitant

For this trial, Rolapitant will be supplied by TerSera as investigationally-labelled commercial supply.

A. Physical Description of Study Drug

Rolapitant will be provided as Rolapitant, 90 mg, (equivalent to 100 mg rolapitant hydrochloride monohydrate) tablets for oral administration. Tablet appearance is blue modified capsule shaped tablet debossed on one side with T0101 and 100 on the other.

B. Packaging, labeling, and Storage

The drug product will be supplied in blister packs containing two (2) 90 mg, (equivalent to 100 mg rolapitant hydrochloride monohydrate) tablets provided by TerSera. Study drug supplies must be stored in a secure, limited-access location under the storage conditions specified on the drug supply label. Rolapitant tablets are stored at Controlled Room temperature, 20-25°C (68-77°F); excursions permitted to 15-30°C (59-86°F) (25).

C. Additional Clinical Supplies

For additional supplies, the pharmacist will coordinate the dispatch of supplies to the site.

D. Drug Accountability

It is the responsibility of the clinical investigator or trained designee to ensure that all study drug received at the site is inventoried and accounted for throughout the study by

the designated personnel and is recorded in the inventory log kept with the pharmacy study documentation. The drug accountability will be verified by a trained designee upon completion of the study. Study drug will be stored in a secured area with restricted access to the dosing preparers only.

The clinical investigator or trained designee must store all study drug pending reconciliation. The investigator agrees that study drug(s) will be dispensed by the investigator or sub-investigator(s) named on the Investigator Agreement or their qualified designees. The investigator, sub-investigators, or qualified designees also agree that the study drug(s) will be dispensed only to study subjects who have provided written informed consent and have met all entry criteria and in accordance with the instructions provided in the pharmacy manual.

After study drug reconciliation, the clinical site may destroy used/unused study drug product locally in accordance with all applicable institutional standard operating procedures, local and federal laws. Documentation of such destruction must be recorded and provided TerSera. If the clinical site does not have the appropriate procedures in place to handle final disposition of clinical supplies, the clinical site will be instructed to return the clinical supplies to TerSera.

3.2 Fosaprepitant

Fosaprepitant iv will be used from the commercial source.

3.3 Other Drugs

Doxorubicin, ifosfamide, vincristine, mesna, and hematopoietic growth factors are all commercially available drugs (see dose modification table in Section 5.3).

4.0 Patient Eligibility

Inclusion Criteria

- Patients with sarcoma which is locally advanced, at high risk for relapse or metastatic for whom treatment with doxorubicin plus ifosfamide (AI) or AI and vincristine (VAI) is indicated.
- Must be 18 to 65 years of age.
- Patient must have an estimated life expectancy ≥ 4 months in the opinion of the investigators.
- Male and Females of child bearing potential must use acceptable methods of birth control which include oral contraceptives, spermicide with either a condom, diaphragm or cervical cap, us of a intrauterine device (IUD) or abstinence.
 - Female patients must have a negative pregnancy test at Screening
 - Female patients of childbearing potential must agree to use an acceptable method of birth control (excluding hormonal birth control methods) for 72

hours prior to admission and to continue its use during the study and for at least 30 days after the final dose

- Male patients must agree to use an acceptable form of birth control from study Day 1 through at least 30 days after the final dose
- Adequate hematologic (ANC > 1500/mm³, platelet count > 100,000/mm³), renal (serum creatinine < 1.5mg/dL), hepatic [serum bilirubin count < 1.5 x upper limit normal (ULN) and SGOT or SGPT < 2.5 x ULN, for subjects with known liver metastases < 5 x ULN] functions.
- Karnofsky Performance Status > 60%. (Appendix D)
- Signed informed consent form.
- Patients are required to read and understand English to comply with protocol requirements.

Exclusion Criteria

- a. Any current treatment, medical history, or uncontrolled condition, other than malignancy, (e.g., alcoholism or signs of alcohol abuse, seizure disorder, medical or psychiatric condition) that, in the opinion of the investigator, would confound the results of the study or pose any unwarranted risk in administering study drug to the subject
- b. Patient has a known hypersensitivity to the administration of any prescribed oral or intravenous study medication or metabolite, including but not limited to, a history of hypersensitivity to the drugs or their components, severe renal impairment, severe bone marrow suppression, or systemic infection
- c. Patient is a woman with a positive urine or serum pregnancy test within 3 days prior to study drug administration, is breast-feeding, or is planning to conceive children within the projected duration of the study treatment
- d. Patient has taken the anti-emetic agents within the last 48 hours prior to the start of treatment with study drug:
 - 5-HT₃ antagonists (ondansetron, granisetron, dolasetron, tropisetron, etc.). Palonosetron is not permitted within 7 days prior to administration of investigational product
 - Phenothiazines (prochlorperazine, fluphenazine, perphenazine, thiethylperazine, chlorpromazine, etc.)
 - Benzamides (metoclopramide, alizapride, etc.)
 - Domperidone
 - Cannabinoids
 - NK1 antagonist (aprepitant)
 - Benzodiazepines (lorazepam, alprazolam, etc)
 - herbal medications or preparations in doses designed to ameliorate nausea or emesis
- e. Patient has received systemic corticosteroids or sedative antihistamines (dimenhydrinate, diphenhydramine, etc.) within 72 hours of Day 1 of the study except

as premedication for chemotherapy (e.g., taxanes). Subjects who are receiving inhaled steroids for respiratory conditions or topical steroids for skin disorders can be enrolled

- f. Patient has symptomatic primary or metastatic CNS disease
- g. Patient has ongoing vomiting, retching, dry heaves, or clinically significant nausea caused by any etiology, or has had such symptoms within 24 hours prior to the start of Day 1 of the study intervention, or has a history of anticipatory nausea and vomiting
- h. Patient must not have been dosed with test drug or blinded study drug in another investigational study within 30 days or 5 half-lives of the biologic activity of the test drug, whichever is longer, before the time of first study dose
- i. Patient who is participating in any investigational agent that is not FDA-approved.
- j. Patient has uncontrolled angina, congestive heart failure (New York Heart Association > class II or known ejection fraction < 40%), uncontrolled cardiac arrhythmia or hypertension, or acute myocardial infarction within 3 months.
- k. Prior surgery or radiotherapy (RT) within 2 weeks of study entry.
- I. Psychological, social, familial, or geographical reasons that would prevent scheduled visits and follow-up.

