6.0 Pretreatment Evaluation

- Standard History and Physical examination including weight and height.
- Karnofsky performance status > 60% (PS appendix D)
- Laboratory studies will include a CBC with differential, and platelet count, electrolytes and serum chemistries.
- Serum beta hCG or urinary pregnancy test (when indicated).
- All screening labs/pretreatment evaluations can be done within 30 days before registration.

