
For the analysis of the primary endpoint of the second part of the trial, Fisher exact test will be used to test the difference of CR rates between the two arms. CR rates along with their 95% confidence intervals (CIs) will be estimated by study arm. We will use logistic regression model (28) to assess the effect of patient specific covariates, such as treatment group, gender, etc. on the complete response. The secondary endpoints are the response rates in each of the time periods (0-24 hours, 24 hrs-120 hrs, and 120-240 hours). Logistic regression models using generalized estimating equations (GEE) will be

used to fit the response data to take the intra-patient correlation into account and to compare the differences of the response rates between the two treatment arms and to evaluate the effects of the patient specific covariates(29).

Toxicity data will be summarized by frequency tables for all patients and by treatment arm. For the efficacy endpoint, intent-to-treat analysis will be applied to the eligible patients. For the toxicity endpoint, per-treated analysis will be used to include any patient who received the treatment regardless of the eligibility nor the duration or dose of the treatment received.

If there are missing data, the reasons for missing data will be recorded, and missing-data mechanism will be checked. For data missing at random (MAR), multiple imputation techniques implemented in SAS PROC MI procedure to handle missing data will be used. For data missing not at random (MNAR), methods that add an explicit model for the missing mechanism to the data model will be applied.

The data from the patients who were treated with dexamethasone at 8 mg on Days 2-5 (prior to amendment 2) will be analyzed separately and included in relevant reports.

Randomization

Randomization will be carried out via CORe.

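### Part II: a breach of exclusion d, e or g found after allocation can drop a patient from the efficacy analysis with the arm known. The effect is modest and the repair cheap

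*Combined protocol and SAP*

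**What the plan says.** **Eligibility (section 4.0).** Three exclusions are defined backwards from treatment:
- d, prior anti-emetics including benzodiazepines: "Patient has taken the anti-emetic agents within the last 48 hours prior to the start of treatment with study drug". Palonosetron has a longer window: "Palonosetron is not permitted within 7 days prior to administration of investigational product".
- e, systemic corticosteroids or sedative antihistamines: "within 72 hours of Day 1 of the study except" as chemotherapy premedication.
- g, vomiting, retching or clinically significant nausea, ongoing or where the patient "has had such symptoms within 24 hours prior to the start of Day 1 of the study intervention".

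**Screening (section 6.0).** "All screening labs/pretreatment evaluations can be done within 30 days before registration". The section lists history and physical examination, performance status, laboratory tests and a pregnancy test.

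**Randomisation (section 11.0).** The whole procedure is: "Randomization will be carried out via CORe". Section 5.1 gives the 1:1 ratio. Neither gives an interval to Day 1 or requires eligibility to be confirmed first.

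**Arms (section 5.1).** Rolapitant is given by mouth and fosaprepitant intravenously, with different dexamethasone schedules. No placebo or blinding is described.

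**Analysis set (section 11.0).** "For the efficacy endpoint, intent-to-treat analysis will be applied to the eligible patients". The toxicity analysis, by contrast, keeps every treated patient whether or not eligible. Nothing says when, or by whom, eligibility is judged.

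**The concern.** Whether a patient breaches d, e or g cannot be settled until study drug or Day 1. If allocation comes first, the breach is judged by people who know the arm. Part of that judgement is soft: g turns on whether nausea was clinically significant. Under section 11.0, a patient judged ineligible leaves the efficacy set.

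Recent nausea, or recent use of lorazepam or diphenhydramine, is plausibly related to the outcome, since CR means no emesis and no rescue medication. Lorazepam and diphenhydramine are also on the breakthrough list in section 5.1. Dropping such patients after allocation would be selection on a prognostic factor. Section 5.1 gives avoidance of patient selection bias as the reason for having the control arm, so the analysis rule works against the purpose of randomising.

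**Working it through.** **1. Does the plan close the gap elsewhere?** Section 3.1 (Drug Accountability) allows study drug to be dispensed only to subjects who meet all entry criteria. Dispensing follows allocation, so this clause cannot stop a patient from being randomised too early. It produces patients who are randomised but not dosed. They have no outcome on study drug and fall outside section 9.1, where one dose makes a patient evaluable. Section 11.0 uses a different definition (completion of cycle 1) and replaces those who do not complete it. No passage says how a randomised, undosed patient is counted.

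**2. The plan's own figure.** Inputs from section 11.0: 39 per arm, Fisher's exact test, two-sided 0.05, CR 40% vs 11%. Exact power is the sum, over all pairs (a, b) with Fisher p ≤ 0.05, of Bin(a; n_A, p_A) × Bin(b; n_B, p_B). This gives 0.802, so the stated 80% is reproduced. The sample size is not in question.

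**3. Size of the bias.** The documents give no rate of late ineligibility, so the share f of Arm A removed is an assumption. The extreme case is true CR 11% in both arms, with only Arm A non-responders removed. Then apparent Arm A CR = 0.11/(1 − f). Without replacement, n_A = 39(1 − f), rounded. The sum in step 2 then gives the actual type I error:

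| f | Arm A n, not replaced | Apparent Arm A CR | Type I error, not replaced | Type I error, replaced to 39 |
|---|---|---|---|---|
| 0 | 39 | 11.0% | 0.018 | 0.018 |
| 5% | 37 | 11.6% | 0.029 | 0.019 |
| 10% | 35 | 12.2% | 0.035 | 0.021 |
| 15% | 33 | 12.9% | 0.036 | 0.025 |
| 20% | 31 | 13.8% | 0.037 | 0.030 |

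Part of the rise without replacement comes from unequal arms alone. At 37 vs 39, with 11% in both arms and no selection, the same sum gives 0.027.

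**4. Single-patient shifts.** Removing one Arm A non-responder changes the Fisher p-values as follows:

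| Result | Two-sided p, before → after | One-sided p, before → after |
|---|---|---|
| 13/39 vs 5/39 | 0.058 → 0.033 | 0.0291 → 0.0249 |
| 11/39 vs 4/39 | 0.0825 → 0.0475 | 0.0413 → 0.0363 |
| 10/39 vs 3/39 | 0.065 → 0.036 | 0.0327 → 0.0290 |

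With 39 in each arm the two-sided p is twice the one-sided p. At 38 vs 39 much of the opposite tail is no longer counted. The two-sided drop is therefore mostly due to the unequal split.

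**5. Power.** If late-ineligible patients are lost equally from both arms and not replaced, power at 40% vs 11% is 0.776, 0.743, 0.706 and 0.685 for f = 5%, 10%, 15% and 20% (37, 35, 33 and 31 per arm). If all are kept and, as a worst case, every late-ineligible patient counts as non-CR, the rates become 0.40(1 − f) and 0.11(1 − f). Power is then 0.772, 0.738, 0.702 and 0.663 at 39 per arm, or 0.814, 0.779, 0.740 and 0.699 at 43 per arm (86/2, the stated maximum accrual).

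**The case against.** The strongest reply is that this is an unspecified procedure and not a demonstrated bias. Much of that stands.

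- A reader might infer that section 6.0 lets d, e and g be checked up to 30 days early. It does not. The 30 days cover the screening items listed there, and d, e and g carry their own windows up to dosing or Day 1. The two sections do not conflict.
- A reader might infer that patients will be randomised days before treatment. No passage says so. The plan permits that order but does not prescribe it, and a site could randomise on Day 1.
- The dispensing clause should stop a patient found in breach before dosing. That patient has no CR outcome, so no known non-responder is being removed. The bias in step 3 applies directly only where a patient is dosed and the breach is judged afterwards. For undosed patients, the risk is arm-aware loss of a prognostic group.
- A reader might infer from step 4 that one patient would decide the trial. Those results were chosen at the boundary. Near the planned rates (16/39 vs 4/39), p is 0.004 before and 0.002 after one removal. By exact enumeration, one Arm A removal turns a non-significant result into significance favouring Arm A with probability about 1% at 11% in both arms, and about 6% at 40% vs 11%.
- Knowledge of the arm is inferred from the oral and intravenous routes and the absence of any described blinding. The plan never calls the trial open-label.

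The analysis rule itself does not yield to these points. Restricting efficacy to eligible patients is explicit, and the adjacent toxicity rule shows that the plan distinguishes the two sets.

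**Conclusion.** The point holds for Part II only. Part I has no randomisation, and Part II depends on Part I not stopping early and on the supplying company's consent. The plan leaves d, e and g open until treatment, sets no order between that check and randomisation, and lets a later finding of ineligibility remove a patient from efficacy when the arm is evident.

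The size is modest. Even under the extreme assumption of 5–20% removed, all non-responders, all from Arm A and none replaced, type I error stays at or below about 0.037, because Fisher's test is conservative here. Apparent Arm A CR is inflated by 0.6 to 2.8 percentage points. These figures rest on an assumed frequency and direction; the documents support neither a rate nor a reason for a difference between arms. The change is worth making because the rule is explicit and easily removed, not because a wrong conclusion is likely.

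**What to change.** **Section 11.0:**
- Make the primary Part II efficacy analysis include all randomised patients in their assigned arm.
- Treat an eligibility breach found after randomisation as a protocol deviation that does not remove the patient.
- State how randomised but undosed patients are counted, for example as non-CR, with a sensitivity analysis excluding them.
- Reconcile this with the one-dose definition of evaluable in section 9.1, and with the cycle-1 completion and replacement wording in 11.0.

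**Section 5.1:** require d, e and g to be confirmed in CORe immediately before randomisation, and randomise as close to first dosing as practicable.

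**Cost:** some protocol wording and one checklist step. Section 2.4.6 describes Part II as not yet initiated. Pharmacy would learn the arm later, and estimated CR rates may be slightly lower. Even in the worst case of step 5, power at 39 per arm (0.772–0.663) is close to what unreplaced loss would give under the present rule (0.776–0.685). Late confirmation should itself keep f small.

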5.0 Treatment Plan

5.1 Study Drug Treatment

This study will be conducted in 2 parts, part I and Part II, as follows:

Part I:

This part will be a single-arm phase II study of rolapitant administered as single-dose on Day 1. In this part, we will estimate the preliminary efficacy of rolapitant administered on day 1 by evaluating complete response (CR) in the single arm setting.

Up to 42 patients will be enrolled in part 1 (after the amendment 4) using the Simon's Minimax 2-stage design; 24 patients will be enrolled in the first stage. If \ge 2 out of 24 patients experience CR, additional 18 patients will be enrolled. The trial will be stopped early if less than 8 patients have complete response in nausea/vomiting.

With conclusion of Part 1 of study, communication of Part 1 study results will be presented to TerSera. In addition, publication of Part 1 study results may be presented for poster abstract and/or scientific journal for publication.

The decision to move on to Part II of this study will not depend on the results of the patients who have been treated with dexamethasone at 8 mg on Days 2-5. Rather, if the first part of the trial for the patients who will be treated with dexamethasone at 12 mg on Days 2-5 was not stopped early due to lack of efficacy of rolapitant and TerSera consents to continuation of the trial, the trial will proceed to the second part of the trial.

Treatment Plan:

All patients will receive anti-emetics approximately 1- 2 hrs prior to chemotherapy infusion as follow: Dexamethasone IV daily for 5 days (12 mg on days 1-5, after the amendment 2), Ondansetron (5HT3 receptor antagonist) 16 mg IV daily for 5 days as standard of care, and Rolapitant, 180 mg will be administered PO on Day 1. For 5-days Ifosfamide regimen, the anti-emetics will be given for 6 days.

Part II: This part will be a randomized, 2-arm phase II study of rolapitant vs fosaprepitant. If the trial was not stopped early, then the trial will proceed to the second part.

Assuming 40% and 11% CR rates in Arm A, and Arm B respectively, approximately 78 evaluable subjects will be randomly assigned to receive Rolapitant or fosaprepitant (1:1) administered as a single dose. The fosaprepitant arm will be used as standard arm to prevent patient selection bias.

Treatment Plan:

Patients will be randomized into two treatment arms: Arm A/ investigational arm: single dose of rolapitant n=39. Arm B/ control arm: single dose of fosaprepitant, n=39.

Arm A/ investigational arm: all patients (n=39) will receive anti-emetics approximately 1-2 hrs prior to chemotherapy infusion as follow: Dexamethasone IV daily for 5 days (12 mg on days 1-5), Ondansetron (5HT3 receptor antagonist) 16 mg IV daily for 5 days as standard of care, and Rolapitant, 180 mg will be administered PO on Day 1.

Arm B/control arm: all patients (n=39) will receive anti-emetics approximately 1- 2 hrs prior to chemotherapy infusion as follow: Dexamethasone IV daily for 5 days (12 mg on day 1, and 8 mg on days 2-5), Ondansetron (5HT3 receptor antagonist) 16 mg IV daily for 5 days as standard of care, and Fosaprepitant 150 mg will be administered IV on Day 1.

If patients don't achieve complete response to Fosaprepitant in cycle 1 in the control arm, they can be given 2 doses of fosaprepitant on days 1 and 4 in cycle 2.

Breakthrough nausea/vomiting and concomitant Medications

Patients may take the following agents for breakthrough nausea as needed: Ondansetron, Lorazepam, Diphenhydramine, and Promethazine.

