11.0 Statistical Consideration and Sample Size

Statistical Considerations and Analysis

This is a phase II trial to study the treatment efficacy of rolapitant on nausea/vomiting in patients with sarcoma receiving multi-day chemotherapy with doxorubicin and ifosfamide regimen (AI). This trial will be carried out in two parts. The primary goal of the first part of the trial is to estimate the preliminary efficacy of rolapitant administered as single-dose on Day 1 by evaluating complete response (CR) rate in a single-arm setting. The primary objective of the second part of the trial is to establish the efficacy of rolapitant

administered as single-dose on Day 1 by evaluating CR rate in comparison with the efficacy of fosaprepitant administered as single-dose on Day 1.

Design and sample size/power

Part I: A single-arm phase II study of rolapitant administered as single-dose on Day 1

We will assess the efficacy of rolapitant on nausea/vomiting by evaluating CR rate using the Simon's Minimax 2-stage design (27). A patient will be considered as to have a CR if s/he does not experience chemotherapy related emesis and do not need rescue medication during cycle-1 following initiation chemotherapy. The primary endpoint is CR rate in cycle 1 (days 1-10). In our previous study, we observed 2 (11%) CRs among 18 patients who were treated with the standard of care. Based on the data of the 19 patients currently enrolled into this study, 6 out of 19 patients (32%) experienced CR. Therefore, a CR rate of 11% or less is considered as clinically insignificant, while a CR rate of 32% or higher is considered as clinically significant. When the probability of accepting an ineffective regimen (CR rate ≤ 11%) is 0.05 and the probability of rejecting an effective regimen (CR rate \geq 32%) is 0.05, the Simon Minimax 2-stage design requires 24 patients in the first stage. The drug will be rejected if no more than 2 responses are seen in the first stage. Otherwise, another 18 patients will be accrued. At the end of the trial, the drug will be rejected if no more than 8 responses are observed in a total of 42 evaluable patients (maximum accrual 47 patients; 42 evaluable, potential 10% drop out rate). The trial will be stopped early 50% of the time, and the mean sample size of the trial will be 33 if the true response rate is 11%. Accrual will be halted after the 24th patient is enrolled until 3 or more responses are seen in the first stage.

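### Section 5.1 caps Part I at 42 enrolled patients and omits the dropout allowance in Section 11.0, so at 10% dropout power would be about 0.90 to 0.93 rather than the planned 0.95

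*Combined protocol and SAP*

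**What the plan says.** **Accrual ceiling.** Section 5.1 (Study Drug Treatment, Part I) reads "Up to 42 patients will be enrolled in part 1 (after the amendment 4) using the Simon's Minimax 2-stage design". It splits the 42 into 24 and 18 and allows nothing for dropout. Section 11.0 (Part I) sets its final boundary on 42 evaluable patients and gives "maximum accrual 47 patients; 42 evaluable, potential 10% drop out rate". For Part II, Section 5.1 does express its target of 78 in evaluable subjects, so only Part I turns the evaluable number into an enrolment limit.

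**Design inputs (Section 11.0).** "a CR rate of 11% or less is considered as clinically insignificant", "while a CR rate of 32% or higher is considered as clinically significant", and both error probabilities are set at 0.05. For stage 1, "the Simon Minimax 2-stage design requires 24 patients in the first stage".

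**Decision rules.** Section 11.0: "The drug will be rejected if no more than 2 responses are seen in the first stage". At the end, 8 or fewer responses among 42 evaluable patients reject the drug, so success needs 9. Section 5.1 continues at 2 or more of 24 and treats fewer than 8 responses as failure, so 8 would succeed.

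**Evaluability.** Section 9.1 makes any patient who receives one dose evaluable. Section 11.0, in its Part II paragraph but worded for the study, requires completion of cycle 1. Section 11.0 also halts accrual once the 24th patient is enrolled, without saying whether the 24 in stage 1 must be evaluable.

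**The concern.** One part of the trial cannot have a ceiling of 42 and a ceiling of 47. A team working from the treatment plan would stop at 42 enrolled; enrolling patients 43 to 47 under Section 11.0 would breach Section 5.1. The design has no slack: 42 is the smallest total that meets both stated error limits, so each patient lost under a cap of 42 takes power below 0.95. Part I decides whether the randomized Part II can go ahead, so lower power means a greater chance of wrongly rejecting an effective regimen at that step.

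**Working it through.** **Inputs.** Null CR rate p0 = 0.11, alternative p1 = 0.32, n1 = 24, r1 = 2, n = 42, r = 8, and 10% dropout, all from Section 11.0. The enrolment cap of 42 is from Section 5.1. Section 11.0 reports 19 patients already enrolled in stage 1 of this design, and Section 2.4.6 reports that all 28 patients enrolled so far (9 in the first cohort, 19 in the second) have completed more than one cycle.

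**Formula.** With X1 ~ Bin(n1, p) and X2 ~ Bin(n − n1, p):

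P(accept) = Σ over x = r1+1 to n1 of P(X1 = x) · P(X2 ≥ r + 1 − x)

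This is the type I error at p0 and power at p1. Early stopping has probability P(X1 ≤ r1).

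**Step 1: reproduce the plan.** For 2/24 and 8/42:
- type I error 0.036 (limit 0.05)
- power 0.951 (target 0.95)
- early stopping at p0 0.499 (stated 50%)
- mean sample size at p0 = 24 + (1 − 0.499) × 18 = 33.0 (stated 33)
- accrual 42 / 0.90 = 46.7, rounded up to 47 (stated 47)

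An exhaustive search confirms 42 as the smallest total, with 2/24 and 8/42 as the minimax design. Every Part I figure checked in Section 11.0 is right.

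**Step 2: evaluable patients under a cap of 42.**
- No dropout: 42.
- 10% of those still to be enrolled: 42 − 19 = 23, and 19 + 0.9 × 23 = 39.7, about 40.
- 10% of all 42: 0.9 × 42 = 37.8, so 37 or 38.
- For comparison, 47 accrued with 10% lost: 0.9 × 47 = 42.3, so 42.

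**Step 3: power at p1 with the Section 11.0 boundaries, stage 1 kept at 24 evaluable.**

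| Evaluable | Type I error | Power |
|---|---|---|
| 42 | 0.036 | 0.951 |
| 41 | 0.031 | 0.942 |
| 40 | 0.027 | 0.930 |
| 39 | 0.023 | 0.917 |
| 38 | 0.020 | 0.901 |
| 37 | 0.017 | 0.882 |

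**Step 4: keep all 42 in the denominator.** If dropouts stay in and count as non-responders (an assumption), the effective rate at 10% dropout is 0.9 × 0.32 = 0.288 and power is 0.889. At 5% dropout it is 0.925.

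**Step 5: the Section 5.1 rules read literally** (r1 = 1, r = 7).

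| Evaluable | Type I error | Power |
|---|---|---|
| 42 | 0.084 | 0.979 |
| 38 | 0.052 | 0.952 |
| 37 | 0.045 | 0.941 |

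**The case against.** **A reader might infer that following Section 5.1 forfeits the 95% power, or that the design then cannot deliver its error rates.** The documents do not support that, for three reasons.

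- With 42 enrolled and none lost, the Section 11.0 boundaries give 0.951. Section 11.0 calls the dropout potential and presents 47 as a maximum.
- The figure of 0.90 pairs the Section 5.1 cap with the Section 11.0 cut-off. Under Section 5.1's own rules, power is 0.952 at 38 evaluable. What fails there is the type I error: 0.052 at 38 and 0.084 at 42.
- Applying 10% to all 42 overlooks the 19 patients who are already past cycle 1. Applied to the other 23, it leaves about 40 evaluable and power of 0.930, a loss of about 2 points rather than 5.

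All three stand, and they limit the size of the point.

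**Section 9.1 could make every dosed patient evaluable**, so that 42 dosed means 42 evaluable. This stands only in part. It does not explain why Section 11.0 budgets five extra Part I patients, and counting dropouts as non-responders still lowers power (Step 4).

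**Stage 1 is effectively decided.** Section 11.0 counts 6 responses among the 19, above the 3 it needs to continue. Given those 6, success needs 3 more: P(Bin(23, 0.32) ≥ 3) = 0.990 with all 23 remaining patients evaluable, against P(Bin(21, 0.32) ≥ 3) = 0.983 with 21. The practical loss from here is therefore small if 32% is the true rate, although that rate was taken from the same 19 patients. The accrual conflict and the stated design power still need correcting.

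**Conclusion.** The inconsistency is real and wrong as written: Section 5.1 omits the dropout allowance that Section 11.0 builds into the same part. It is a conflict between sections, not an arithmetic error in Section 11.0.

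Under a cap of 42 and the Section 11.0 boundaries, design power at a 32% CR rate is 0.951 with no losses, about 0.93 with 10% dropout among the 23 patients still to come, and about 0.90 with 10% dropout among all 42. These figures assume that non-evaluable patients leave the denominator, that stage 1 has 24 evaluable patients, and that power is judged at the design stage without conditioning on responses already seen. The type I error stays below 0.05 in each of these cases.

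The decision-rule conflict is linked and must be settled with it, because the accrual ceiling has a known effect on the error rates only once the boundaries are fixed.

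**What to change.** 1. In Section 5.1, replace the cap with a statement that up to 47 patients will be accrued to obtain 42 evaluable patients. Section 11.0 already plans this. If 42 enrolled is the intended limit, amend Section 11.0 instead and restate power as about 0.90 to 0.93 at 10% dropout.
2. Reconcile the decision rules: Section 5.1 continues at 2 or more of 24 and fails below 8; Section 11.0 continues at 3 or more of 24 and rejects at 8 or fewer of 42. Only the Section 11.0 pair reproduces the stated error rates.
3. State whether the 24 in stage 1 are enrolled or evaluable patients.
4. State which evaluability definition governs Part I: one dose (Section 9.1) or completion of cycle 1 (Section 11.0).

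The cost is a few sentences in one amendment. Keeping to Section 11.0 adds no patients beyond those it already allows. At the status the document reports (19 of the 24 stage 1 patients enrolled), the change can be made before the cap takes effect.
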